#### **SJM Implantable pulse generator**

The IPG is a 16 channel, multi-programmable system designed to be connected to a lead arrangement containing either 4 or 8 electrodes. It is powered by a hermetically sealed battery within a titanium case and uses microelectronic circuitry to generate constant current electrical stimulation. The battery can be a primary cell or a rechargeable lithium ion battery. Stimulation programs can be delivered as either single stimulation or MultiStim™ programs depending on the subject's needs.

#### **SJM Leads**

Leads consist in arrays or grids of platinum-iridium electrodes encased in a silicone sheath. Any commercially available SCS SJM lead may be used in the study.

#### **SJM Extensions**

Extensions are designed to connect the lead to the IPG. One end of the extension is designed to receive the proximal end of the lead, and the opposite end of the extension is designed for insertion and connection with the IPG. Any commercially available SCS SJM lead may be used in the study.

#### **SJM IPG Recharger**

The IPG Charging System provides the capability to recharge the IPG battery while stimulation is either on or off. The charging system has several main parts: AC line cord, AC power supply, power cable, and charger antenna. The charger transmits RF energy through the antenna to the IPG battery to recharge it. Only subjects with implanted rechargeable IPGs will use IPG rechargers.

#### **SJM Clinician Programmer**

## Clinical Investigational Plan

The Clinician Programmer system is a programming component of the SCS system and is intended to provide a rapid and efficient means of programming. It is designed to be used by clinicians for the purpose of collection/transfer of stimulation parameters and noninvasive control of programmer function. The Clinician Programmer system uses a touch screen to program the stimulator to the required waveforms and electrode configurations and to log the information derived.

### 5.2 DEVICE ACCOUNTABILITY (if applicable)

Devices used in this study are market released and implanted in the patients prior to enrollment. So device accountability is not required.

## Clinical Investigational Plan

### 6.0 PROCEDURES

#### 6.1 STUDY FLOW CHART

[figure not shown]

Figure 2: Flow Chart of the study

## Clinical Investigational Plan

### 6.2 PROCEDURES

The clinical study will be conducted in accordance with the CIP. All parties participating in the conduct of the clinical study will be qualified by education, training, or experience to perform their tasks and this training will be documented appropriately.

The clinical study will not commence until St. Jude Medical receives written approval from the EC and relevant regulatory authorities and all required documents have been collected from the site(s).

Table 1: List of all study specific activities/procedures

Study Activity	Visit	Screening	Follow up visit 1	Follow up visit 2	Follow up visit 3
Informed Consent		X			
Inclusion/Exclusion Criteria Screening		X			
Randomization		X			
Sequester patient programmer		X			
Return patient programmer					X
Provide pain diary		X	X	X	
Collect pain diary			X	X	X
VAS assessment			X	X	X
EQ-5D questionnaire			X	X	X
Subject satisfaction questionnaire			X	X	X
Collect programming parameter printouts			X	X	X
Stimulation reprogramming		X	X	X	
Document patient preference					X
Program preferred stimulation paradigm					X

Table 2: Visits Timeline

Visit	Screening	Follow up visit 1	Follow up visit 2	Follow up visit 3
Timing	At enrollment	14±5 days after screening visit	14±5 days after follow up visit 1	14±5 days after follow up visit 2

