## Clinical Investigational Plan

paradigm. One week after this visit, the subject will be contacted to schedule the first follow up visit and instructed to start recording pain levels on the pain diary.

Two weeks after the screening visit, the subject will visit the clinic for the first follow up assessment. A Visual Analog Scale (VAS) score will be collected to determine pain levels during the first stimulation paradigm; the subject will also fill the EQ-5D and the satisfaction questionnaires administered by a clinician who is blinded to the stimulation paradigm. Subject's stimulators will be programmed with the second stimulation paradigm according to the group assignment. Stimulation intensity will gradually be increased until the subject perceives the stimulation to find the Threshold for Perception (TP), and then the intensity will subsequently be reduced to the sub-perception level providing optimal pain relief. Subjects will return the pain diary and will be provided with a new one for the assessment of the new stimulation paradigm. One week after this visit, the subject will be contacted to schedule the second follow up visit and instructed to start recording pain levels on the pain diary

Two weeks after the first follow up visit, the patient will return for the second follow up visit during which the efficacy of the second stimulation paradigm will be evaluated using the VAS, the EQ-5D and the subject satisfaction assessments administered by a clinician blinded to the stimulation paradigm. Subject's stimulators will be programmed with the third stimulation paradigm according to the group assignment. Stimulation intensity will gradually be increased until the subject perceives the stimulation to find the Threshold for Perception (TP), and then the intensity will subsequently be reduced to the sub-perception level providing optimal pain relief. Subjects will return the pain diary and will be provided with a new one for the assessment of the new stimulation paradigm. One week after this visit, the subject will be contacted to schedule the third follow up visit and instructed to start recording pain levels on the pain diary

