Two weeks after the second follow up visit, the subject will return for the third follow up visit where the efficacy of the third stimulation paradigm will be assessed using the VAS, the EQ-5D and the subject satisfaction assessment. Subject will return the last pain diary and will be asked to specify their preference between the three different stimulation paradigms. After all activities are completed, the subject will exit the study.

Any unscheduled visits that occur within the study, and the reason for the visit will be documented. Stimulation related adverse events will be recorded throughout a subject's participation in the study.

The duration of each subject participation is expected to be between 6 and 8 weeks; the duration for the study is expected to be 6 months.

The clinical study will be conducted at a maximum of four centers in the European Union (EU).

An envelope-based system will be used for identifying which group the subject has been assigned. St. Jude Medical will provide sealed envelopes containing the site number and subject ID/sequence number. Inside the envelope, the randomization assignment will be identified along with the site number and subject ID/sequence number.

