### Clinical Investigational Plan

Enrollment activities must be performed before any other study procedure/visit. Enrollment information (name of the study, date of consent) should be recorded in the clinic records, and the Enrollment form should be completed and submitted in a timely manner (recommended within 5 days). Notification of enrollment to the sponsor will take place only when the sponsor receives the Enrollment form.

In case the subject was consented, but does not meet inclusion/exclusion criteria, the following actions will be taken:

If additional study procedures have not occurred:

- Document enrollment information (name of the study, date of consent) and inclusion/exclusion information in the clinic and/or study records; complete the Enrollment Form and all forms for the Screening visit. The forms must be authorized / approved by the principal or delegated investigator.
- The EC should be notified appropriately about any deviations with regards to obtaining the informed consent.

If additional study procedures have occurred:

- Document enrollment information (name of the study, date of consent) and inclusion/exclusion information in the clinic and/or study records; complete the Enrollment Form, all forms for the Screening visit, and the Withdrawal Forms. The forms must be authorized / approved by the principal or delegated investigator.
- Complete study deviation for inclusion/exclusion not met.
- The EC should be notified appropriately about any deviations with regards to obtaining the informed consent.

If the subject meets the inclusion/exclusion criteria, the patient programmer will be sequestered and the subjects will be provided a one-week pain diary. Subjects will be randomized to one of the three treatment groups and their stimulator will be programmed with the first stimulation paradigm according to the group assignment. Stimulation intensity will gradually be increased until the subject perceives the stimulation to find the Threshold for Perception (TP), and then the intensity will subsequently be reduced to the sub-perception level providing optimal pain relief. Subjects will then receive a one-week pain diary to assess the pain levels during the first assigned stimulation paradigm. One week after this visit, the subject will be contacted to schedule the first follow up visit and instructed to start recording pain levels on the pain diary.

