Note: If a subject misses one or more of the scheduled follow up visits (inclusive of the assigned visit windows), this will be considered as a missed visit. If subject misses a visit, the subject will be asked to fill the one week pain diary again and the latest pain diary will be used for analysis. The subject may therefore still return for subsequent visits and will not be excluded from the study.

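### The visit window in Table 2 opens before the one-week pain diary can be complete, and no rule restores the lost diary days

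*Combined protocol and SAP*

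**What the plan says.** Section 6.2, Table 2, times the three follow-up visits at "14±5 days after screening visit", "14±5 days after follow up visit 1" and "14±5 days after follow up visit 2".

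The diary instruction is in section 4.2 and again in section 6.3: "One week after this visit, the subject will be contacted to schedule the first follow up visit and instructed to start recording pain levels". Sections 6.4 and 6.5 repeat it for the second and third paradigms. One contact therefore does two things: it books the visit and it starts the diary. Table 1 and sections 6.4 to 6.6 have the diary collected at the visit that ends the period. At visits 1 and 2 the stimulator is reprogrammed at that same visit.

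Section 6.11 provides for a repeat diary when a visit is missed, and says that "the latest pain diary will be used for analysis". A visit counts as missed only after its window has been taken into account.

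On total time in the study, section 4.2 says: "The duration of each subject participation is expected to be between 6 and 8 weeks".

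**The concern.** The diary is meant to measure pain under each paradigm over a week, but the visit schedule permits its collection before that week has passed. A site can follow every written rule and still return a diary with two or three entries. Once the next paradigm is programmed, the missing days for the previous one cannot be recovered.

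How complete a diary is would then depend on when the visit happened to be booked, and could differ between the three periods of one subject. In a three-period crossover the comparison is made within subjects, so a seven-day mean under one paradigm might be set against a two-day mean under another. The same window lets the length of the periods differ within a subject.

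**Working it through.** **Inputs**
- Interval between consecutive visits: 14 ± 5 days (Table 2), so 9 to 19 days, which is 11 permitted days.
- Contact and diary start: day 7 after the programming visit (sections 4.2, 6.3, 6.4, 6.5). I take the contact as made exactly on day 7.
- Diary length: 7 days (sections 4.2 and 6.3).
- Diary collected at the next visit (Table 1; sections 6.4 to 6.6).
- Expected participation: 6 to 8 weeks, that is 42 to 56 days (section 4.2).

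**Diary days available at the visit**

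With recording from day 7 and the visit day not counted, diary days = min(7, visit day − 7). The plan does not say how to count, so two alternatives are shown: counting the visit day, min(7, visit day − 6); and making the first entry on day 8 without counting the visit day, min(7, visit day − 8).

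| Visit day | Start day 7 | Visit day also counted | First entry day 8 |
|---|---|---|---|
| 9 | 2 | 3 | 1 |
| 10 | 3 | 4 | 2 |
| 11 | 4 | 5 | 3 |
| 12 | 5 | 6 | 4 |
| 13 | 6 | 7 | 5 |
| 14 | 7 | 7 | 6 |
| 15 to 19 | 7 | 7 | 7 |

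Under the main convention, days 9 to 13 give an incomplete diary: 5 of 11 permitted days, 5/11 = 45%. The alternatives give 4/11 = 36% and 6/11 = 55%. The convention shifts the boundary by one day either way and does not remove the conflict. These fractions count calendar days in the window. They become shares of visits only if visits are spread evenly over it. Without that assumption the share lies anywhere from 0% (all visits late enough) to 100% (all visits early).

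**Is there a safeguard?**

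The repeat diary in section 6.11 is triggered by a missed visit. A day-9 visit is inside the window, so it is not missed and nothing is triggered. No section sets a minimum number of diary days or requires a complete diary before the visit.

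**Period length**

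Longest over shortest permitted period: 19/9 = 2.1. This is the extreme case within one subject.

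**Total participation**
- Nominal: 3 × 14 = 42 days = 6.0 weeks, which reproduces the lower end of the stated range.
- All visits earliest: 3 × 9 = 27 days = 3.9 weeks, which is 42 − 27 = 15 days below the stated range.
- All visits latest: 3 × 19 = 57 days = 8.1 weeks, which is 57 − 56 = 1 day above it.

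**The case against.** The strongest reply is that the contact on day 7 both books the visit and starts a one-week diary. A site handing out a seven-day task would have little reason to book the visit two days later, so early visits may be uncommon and an even spread over the window is implausible. That is fair as to frequency, and it is why the 45% should be read only as an illustration. It does not remove the conflict, because the written rules still permit the early booking.

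A second reply is that the diary carries little weight. The endpoints in section 4.4 do not name it, and section 12.1 names the VAS, EQ-5D, satisfaction and preference. The VAS is collected separately at the visit and loses nothing when the diary is short. This stands and limits the severity. But the diary cannot be dismissed as unused: section 6.11 says it enters the analysis, and sections 4.2 and 6.3 give its purpose as assessing pain under the assigned paradigm.

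Third, this is a feasibility study with no formal power target (section 12.2), so some loose ends are tolerable. That also supports a low rating.

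Three stronger readings are tempting and are not supported:
- A reader might infer that the window contradicts the stated participation time. Section 4.2 gives an expected range, the nominal schedule falls inside it, and the 27-day extreme needs all three visits at their earliest. It is a loose fit, almost all of it at the lower end.
- A reader might infer that short periods bias the comparison towards no difference through carry-over. The documents give no carry-over duration, so nothing shows that 9 days is too short or that 14 is enough.
- A reader might infer that the remedy is simply to close the early half of the window. That would still allow 57 days against 56. Because these visits are also when stimulation is reprogrammed, it would set the length of the treatment periods, which is for the sponsor to decide.

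**Conclusion.** The point holds as a conflict between Table 2 and the diary procedure. A compliant visit on days 9 to 13 yields about 2 to 6 of 7 diary days, and at day 9 the figure is 1 to 3 depending on how days are counted. The same is possible in all three periods, and no rule repairs it.

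This rests on the contact being made on day 7, the diary starting then, and collection at the visit. All three are stated in the plan. The number of visits affected cannot be derived from the documents: 0 to 100%, with 45% only under an even spread.

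The consequence is confined to the diary data, whose role in the analysis is itself thinly defined. Period length may vary from 9 to 19 days within a subject, which does bear on when the VAS is taken, but the effect cannot be sized. The participation range of 27 to 57 days against an expected 42 to 56 is a minor inconsistency. Overall: low severity, worth correcting because correction is cheap.

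**What to change.** Reconcile Table 2, the diary-start instruction (sections 4.2 and 6.3 to 6.5) and the expected duration (section 4.2), so that no in-window visit can precede completion of the seven diary days.

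One way is to use the existing contact. When the site tells the subject to start the diary, require the appointment to be booked after the seventh diary day. State which day counts as the first entry and whether the visit day counts, since under one convention even a day-14 visit gives only 6 days.

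Record the actual length of each period and the number of completed diary days on the case report form, and say in section 12.1 how they will be used when the diary is analysed.

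The cost is a small amendment, with ethics committee notification or approval if required (section 14.0), two data items per period, and somewhat less scheduling freedom for sites. If the reconciliation narrows the window, more visits may count as missed under section 6.11 and trigger a repeat diary. Leaving the window as it is and adding only the booking rule and the two data items would keep that to a minimum.

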### 6.3 SCREENING VISIT

Enrollment of subjects will occur at the investigational sites subsequent to obtaining the EC and site-specific (if needed) approvals. Patients recommended by the Principal Investigator at the study site as a candidate and who meet the standard requirements will be approached to participate in this study. The patient will be informed about the study to determine if he/she is interested in participating. Patients who are interested in participating will first sign the informed consent form. Once the patient signs the informed consent form, they become a subject in the study.

### Clinical Investigational Plan

Enrollment activities must be performed before any other study procedure/visit. Enrollment information (name of the study, date of consent) should be recorded in the clinic records, and the Enrollment form should be completed and submitted in a timely manner (recommended within 5 days). Notification of enrollment to the sponsor will take place only when the sponsor receives the Enrollment form.

In case the subject was consented, but does not meet inclusion/exclusion criteria, the following actions will be taken:

If additional study procedures have not occurred:

- Document enrollment information (name of the study, date of consent) and inclusion/exclusion information in the clinic and/or study records; complete the Enrollment Form and all forms for the Screening visit. The forms must be authorized / approved by the principal or delegated investigator.
- The EC should be notified appropriately about any deviations with regards to obtaining the informed consent.

If additional study procedures have occurred:

- Document enrollment information (name of the study, date of consent) and inclusion/exclusion information in the clinic and/or study records; complete the Enrollment Form, all forms for the Screening visit, and the Withdrawal Forms. The forms must be authorized / approved by the principal or delegated investigator.
- Complete study deviation for inclusion/exclusion not met.
- The EC should be notified appropriately about any deviations with regards to obtaining the informed consent.

If the subject meets the inclusion/exclusion criteria, the patient programmer will be sequestered and the subjects will be provided a one-week pain diary. Subjects will be randomized to one of the three treatment groups and their stimulator will be programmed with the first stimulation paradigm according to the group assignment. Stimulation intensity will gradually be increased until the subject perceives the stimulation to find the Threshold for Perception (TP), and then the intensity will subsequently be reduced to the sub-perception level providing optimal pain relief. Subjects will then receive a one-week pain diary to assess the pain levels during the first assigned stimulation paradigm. One week after this visit, the subject will be contacted to schedule the first follow up visit and instructed to start recording pain levels on the pain diary.

NOTE: As soon as the subject signs the Patient Informed Consent, adverse events need to be reported according to the guidelines mentioned in section 8.2.

The following activities and assessments will be performed during screening visit.

Timing of visit	Activities at visit	Case Report Form
Screening	
 
● Subject signs informed consent
 
● Subject is screened for inclusion/exclusion criteria
 
● Sequester Patient Programmer
 
● Provide pain diary
 
● Randomization
 
● Program IPG with first stimulation paradigm according to group assignment
 
	
 
● Enrollment Form
 
● Inclusion/Exclusion Form
 
● Randomization Parameters Form
 

## Clinical Investigational Plan

### 6.4 FOLLOW UP VISIT 1

During the baseline visit, the investigator will collect the pain diary provided at the screening visit and record the current stimulation parameters in the parameters form. The subject will rate the pain during the first stimulation paradigm using the VAS, the EQ-5D and the satisfaction questionnaires administered by a clinician blinded to the stimulation paradigm. Subject’s stimulators will be programmed with the second stimulation paradigm according to the group assignment. Stimulation intensity will gradually be increased until the subject perceives the stimulation to find the Threshold for Perception (TP), and then the intensity will subsequently be reduced to the sub-perception level providing optimal pain relief. Subjects will be provided with a new pain diary for the assessment of the new stimulation paradigm. One week after this visit, the subject will be contacted to schedule the second follow up visit and instructed to start recording pain levels on the pain diary

The following activities and assessments will be performed during the first follow up visit.

Timing of visit	Activities at visit	Case Report Form
Follow up 1	
 
Collect pain diary
 
Programming parameters printout
 
Subject fills out pain assessment and quality of life questionnaires
 
Provide pain diary
 
Program IPG with second stimulation paradigm according to group assignment
 
	
 
VAS Form
 
EQ-5D Form
 
User Satisfaction Form
 
Parameters Form
 

### 6.5 FOLLOW UP VISIT 2

During the second follow up visit, the investigator will collect the pain diary provided at the first follow up visit and record the current stimulation parameters in the parameters form. The subject will rate the pain during the first burst microdosing stimulation paradigm using the VAS, the EQ-5D and the satisfaction questionnaires administered by a clinician blinded to the stimulation paradigm. Subject’s stimulators will be programmed with the third stimulation paradigm according to the group assignment. Stimulation intensity will gradually be increased until the subject perceives the stimulation to find the Threshold for Perception (TP), and then the intensity will subsequently be reduced to the sub-perception level providing optimal pain relief. Subjects will be provided with a new pain diary for the assessment of the new stimulation paradigm. One week after this visit, the subject will be contacted to schedule the third follow up visit and instructed to start recording pain levels on the pain diary

The following activities and assessments will be performed during the second follow up visit:

Timing of visit	Activities at visit	Case Report Form
Follow up 2	
 
Collect pain diary
 
Programming parameters printout
 
Subject fills out pain assessment and quality of life questionnaires
 
Provide pain diary
 
Program IPG with third stimulation
 
	
 
VAS Form
 
EQ-5D Form
 
User Satisfaction Form
 
Parameters Form
 

